# 7.2. Discussion of Study Design

Subjects with opioid physical dependence and moderate to severe opioid use disorder (based on criteria defined in the Diagnostic and Statistical Manual of Mental Disorders - Fifth Edition [DSM-V]) will be enrolled in this study. Because this is the intended patient population, results from this study will be directly applicable to the therapeutic use of CAM2038 q1w in clinical practice (i.e., determine the ability of CAM2038 q1w to block illicit opioid effects, which is one dimension of opioid maintenance treatment). These subjects are also likely to provide meaningful ratings of subjective opioid effects based on their prior opioid use experience. For ethical and safety reasons, non-dependent opioid users will not be included, as they are less likely to tolerate the higher CAM2038 q1w doses (i.e., no naltrexone blockade) and because it would be unethical to produce opioid dependence in an opioid abuser who are not currently physically dependent. In addition to the requirement that subjects are "history-qualified" (i.e., history of regular opioid use), this study will use a pharmacologic qualification to ensure that subjects who meet the drug use history criteria can also distinguish and demonstrate "liking" of the subjective euphoric experience of both doses of hydromorphone compared to placebo. Therefore, the pharmacologic qualification procedure provides a more objective confirmation of drug use history and ensures that subjects can respond appropriately in a laboratory setting as well as tolerate the doses of hydromorphone.

Subjects will be carefully screened to eliminate those presenting with a clinically significant history of seizure disorders, history of asthma or other respiratory disorders, head injury, hypertension or personal history of cardiovascular disease or clinically significant electrocardiogram (ECG). Subjects must not have clinically significant chronic illness (e.g., diabetes, liver or kidney disease). Subjects with a known hypersensitivity to any of the study drugs or to specific opioids will not be enrolled.

Studies with opioid-dependent subjects have used a wide array of opioid maintenance drugs and doses to stabilize subjects. In the current study, all subjects will be stabilized on a 30 mg dose of IR morphine, administered QID (with the option of adding one additional dose of IR morphine during the first 3 days of stabilization, as needed) prior to enrollment in the Treatment Phase. Administration of IR morphine 30 mg will ensure that any opioids that the subject may have recently used will be washed out and will also establish a consistent schedule of opioid administration, thereby shortening the duration of opioid washout period required prior to administration of the Qualification/Baseline Hydromorphone Challenge Session. Therapeutically, patients will be induced with CAM2038 q1w immediately after a short period of abstinence (approximately 12 hours) from opioid use as is typical for induction onto buprenorphine; therefore, to remain consistent with how the product will be administered clinically, a short-acting opioid (morphine sulfate) has been selected for stabilization purposes.

In addition, the 3 to 7 day IR morphine 30 mg stabilization phase will ensure that any opioids used prior to check-in will be sufficiently washed out, while also increasing the likelihood that subjects will have a similar level of physical dependence to opioids prior to beginning the Qualification/Baseline Hydromorphone Challenge. The intention of stabilizing all subjects on IR

Version: 2.0, 17NOV2015 Page 41 of 99

morphine 30 mg is to attempt to decrease the severity of and discomfort associated with opioid withdrawal (Walsh et al., 2015). This will increase the validity of baseline measurement of "drug liking" collected after the first administration of hydromorphone (i.e., baseline scores will be less likely to be skewed in either direction due to severe withdrawal effects).

Many studies have evaluated the conditions under which buprenorphine can be administered to opioid dependent individuals to avoid the precipitation of withdrawal. Collectively, these studies have shown that BPN-precipitated withdrawal is dependent on the following: 1) duration of action of the maintenance opioid (whereby precipitated withdrawal is more likely to occur in those maintained on long-acting opioids (e.g., methadone) than short-acting opioids (e.g., heroin), 2) the time since last opioid maintenance dose (whereby precipitated withdrawal is more likely to occur when opioid dosing is recent and more opioid is on board than when time for opioid wash-out has occurred and the individual is showing signs of opioid withdrawal, and 3) the absolute dose of BPN (whereby a higher BPN dose is more likely to precipitate withdrawal compared to a lower dose of BPN). The strategy proposed here addressed each of these principles in the following manner: 1) Subjects will be maintained on a short-acting opioid, morphine, rather than a long-acting opioid, 2) Morphine will be omitted for a period of ~12 hours and withdrawal signs and symptoms are expected to emerge during this interval prior to CAM2038 q1w administration (subjects will be required to score 8 points or greater on the COWS prior to being dosed with CAM2038 glw on Day 0 (Walsh et al., 2015), and 3) while the absolute depot dose of CAM2038 q1w at 24 and 32 mg is high, the more relevant factor is the initial concentration exposures following the injection and the rate of onset, whereby a slower rate of BPN delivery is associated with decreased likelihood of precipitated withdrawal (Rosado et al., 2007). The standard recommended approach (although not necessarily the most commonly used in clinical practice) is to begin dosing with 4 mg, wait for 2 hours and, in the absence of precipitated withdrawal, administer an additional 4 mg. A 4 mg sublingual tablet of BPN will produce a concentration of approximately 2 ng/mL (Cmax) at approximately 1 hour post-dose (Ciraulo et al., 2006), while an 8 mg initial dose would produce ~4.3 ng/mL (Cmax) at approximately 1.5 hour post-dose (HS-11-426). With respect to the CAM2038 q1w doses proposed for testing here, even at the highest dose (32 mg), BPN plasma levels will not exceed 2 ng/mL until approximately ~4 hours after administration. Thus, the initial BPN concentration exposure is predicted to be lower than the exposure typically seen during the first 2-4 hours of initial induction with SL products. Moreover, with CAM2038 q1w, concentrations will continue to slowly rise, reaching Cmax at approximately 24 hours post-dose. While BPN-precipitated withdrawal is a relatively rare occurrence in clinical practice, one strategy employed for treatment is to give more BPN. Given the pharmacokinetics of CAM2038 q1w, this potential approach for treating BPN-precipitated withdrawal is built into the product design and may serve to ameliorate any potential withdrawal effects. However, if withdrawal does occur, specific procedures have been included to ensure that subjects are assessed and receive treatment for symptoms (See Section 10.6).

The overall design of the current study is consistent with previously published opioid agonist challenge studies, which have investigated the opiate blocking effects of BPN (Jasinski et al., 1978; Walsh et al., 1995). Based on the pharmacokinetic profile of CAM2038 q1w, specifically that BPN peak plasma concentrations are observed within the first 24 hours post-dose,

Version: 2.0, 17NOV2015 Page 42 of 99

Hydromorphone Challenge Sessions will begin a minimum of 24 hours following the first dose of CAM2038 q1w. An additional Hydromorphone Challenge Session will be administered after 48, 72, 96, 120, and 144 hours post-dose in order to investigate the full duration and magnitude of opioid-blockade of the CAM2038 q1w formulation. In order to improve subject retention, the study drug will be administered for two weeks with two sets of three Hydromorphone Challenge Sessions per week; thereby reducing the inpatient Treatment Phase and the overall duration of the study.

In the current study, subjective "at the moment" assessments using VAS for Drug Liking, Feeling High, Any Drug Effects, Good Drug Effects, Bad Drug Effects, Sedated, and Desire to Use Opioids will be included to measure the degree and time course of the CAM2038 q1w-induced blockade of subjective effects. In addition, pharmacokinetic samples will be collected on each Hydromorphone Challenge Session day to measure plasma levels of BPN and norbuprenorphine prior to the challenge session.

Randomization will be used to avoid bias in the assignment of treatment for all the Hydromorphone Challenge Sessions and in the assignment of subjects to the 24 mg or 32 mg CAM2038 q1w dose groups during the Treatment Phase. Prior to the Qualification/Baseline Hydromorphone Challenge Session, subjects will be randomized to 1 of 6 challenge sequences, according to two 3 x 3 William squares (ABC, ACB, BAC, BCA, CAB, CBA), and will receive one dose of hydromorphone daily over 3 consecutive days, including 2 doses of hydromorphone and 1 dose of placebo. This approach has previously been shown to be sensitive to identifying dose-related agonist effects, while ensuring that both subjects and staff remain blinded to the dose of hydromorphone or placebo being administered, thereby reducing the risk of potential expectancy effects. As an additional precaution, subjects will be housed in inpatient research units for the duration of the study both for safety monitoring and to ensure that the subjects do not use other illicit opioids while enrolled in the study, as this may affect the Hydromorphone Challenge Session results.

Randomization increases the likelihood that known and unknown subject attributes (e.g., demographics and baseline characteristics) will be evenly balanced across dose groups and enhance the validity of statistical comparisons across dose groups. It was not possible to include a placebo control group (CAM2038 SC Placebo injection) in the current study because the enrolled population will be physically dependent on opioids and would go into opioid withdrawal with placebo administration. Therefore, this study includes a Qualification/Baseline Hydromorphone Challenge Session to establish the frequency and magnitude of changes in clinical endpoints that may occur in the absence of CAM2038 q1w.

Version: 2.0, 17NOV2015 Page 43 of 99

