### 7. INVESTIGATIONAL PLAN

# 7.1. Overall Study Design and Plan

This is a multi-site, randomized, double-blind, repeat-dose Phase 2 study to evaluate the degree and duration of action of multiple doses of CAM2038 q1w in blocking the effects of a mu opioid agonist (hydromorphone) in patients with moderate or severe opioid use disorder. The study will involve 4 phases: Screening, Qualification, Treatment, and Follow-up.

Within 4 weeks of initiating screening, subjects will be admitted to a clinical research unit (CRU) for the Qualification Phase. Following check in to the CRU, subjects will be transitioned to a short-acting oral opioid, IR morphine 30 mg, (administered 4 times daily [QID]), for a minimum of 3 days and a maximum of 7 days (Qualification Phase described in detail in Section 7.1.2). One additional dose of IR morphine 30 mg may be administered for the first 3 days of stabilization, as needed, at the investigator's discretion. After stabilization on IR morphine 30 mg, all subjects will complete a 3-day Qualification/Baseline Hydromorphone Challenge Session which will involve IM administration of 3 doses of hydromorphone (Treatment A: 0 mg [placebo], Treatment B: 6 mg and Treatment C: 18 mg) administered once daily (Day -3, Day -2, and Day -1) in a randomized, double blind, crossover manner, with each hydromorphone administration separated by approximately 24 hours (described in detail in Section 7.1.4).

Following the Qualification/Baseline Hydromorphone Challenge Session, eligible subjects will receive CAM2038 q1w at doses of 24 mg or 32 mg (randomized in a 1:1 ratio to 1 of 2 groups). Subjects will receive once weekly SC injections of CAM2038 q1w for 2 weeks (injections on Day 0 and Day 7) and will remain inpatient in the CRU for up to 25 days (including Qualification Phase), during which time 4 Hydromorphone Challenge Sessions (3 consecutive days each) will be conducted on Days 1 to 3, Days 4 to 6, Days 8 to 10, and Days 11 to 13, respectively. Safety and pharmacodynamic assessments will be performed on each day of the Hydromorphone Challenge Sessions at multiple timepoints beginning at pre-dose until approximately 5 hours post-dose. Plasma samples to quantify BPN and norbuprenorphine levels will also be obtained approximately 60 minutes prior to hydromorphone dosing on each day of the Hydromorphone Challenge Sessions.

Subjects will be discharged on Day 14 and a follow-up phone interview will be conducted on approximately Day 21.

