#### 7.1.3. Treatment Phase

#### 7.1.3.1. Days 0 to 6

On the morning of Day 0 of the Treatment Phase, subjects will receive one of the following treatments (based on randomization in a 1:1 ratio, stratified by gender) to:

- Group A: CAM2038 q1w 24 mg SC injection
- Group B: CAM2038 q1w 32 mg SC injection

Maintenance IR morphine 30 mg will be withheld for at least 12 hours prior to CAM2038 q1w dosing; therefore, the Day -1 evening dose and the Day 0 morning dose of IR morphine 30 mg will be withheld. The Clinical Opiate Withdrawal Scale (COWS; See Section 17.2) will be administered prior to dosing with CAM2038 q1w; in order to be dosed on Day 0, subjects will be required to have a COWS score of  $\geq 8$ , indicative of mild withdrawal.

CAM2038 q1w treatment will be administered at approximately 9:00 am; CAM2038 q1w administration instructions for user (IFU) will be provided in the Manual of Procedures (MOP).

On Days 1 to 3 and Days 4 to 6, subjects will undergo 2 separate Hydromorphone Challenge Sessions (described in Section 7.1.4), with each daily challenge dose of IM hydromorphone administered at approximately 9:00 am (i.e., approximately 24, 48, 72, 96, 120, and 144 hours following Day 0 CAM2038 q1w injection). Safety and pharmacodynamic assessments will be conducted immediately following each dose of hydromorphone administered in each Hydromorphone Challenge Session (maximum 5 hours after Hydromorphone Challenge Session). Plasma samples will also be collected prior to hydromorphone dosing on each day of the Hydromorphone Challenge Sessions.

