### 7.1.5. Follow-up Phase

Following the last day of the Treatment Phase (i.e., Day 14), plasma BPN levels are expected to be approximately 1.4 to 1.8 ng/mL and to gradually taper off; therefore, subjects are not expected to experience immediate withdrawal effects at the time of discharge. A follow-up telephone interview will be conducted approximately 7 days after discharge from the CRU to obtain information on any safety issues including withdrawal effects.

Subjects will participate in the study for approximately 7 weeks, from Screening to Follow-up.

An overview of the study design is provided in Figure 2.

Study assessments and procedures will be performed at the visits and time points outlined in the Schedule of Assessments.

Section 10 provides additional information on the baseline, safety, and pharmacodynamic procedures and assessments included in the study. Pharmacodynamic endpoints are described in Section 10.7. Statistical analysis is described in Section 12.

Version: 2.0, 17NOV2015 Page 35 of 99

Figure 2 Overview of Study Design

Screening	Qualif	ication		Treat	ment		Follow-up
	Inpatient Start	Qualification/ Baseline Challenge	q1w Dose 1	Week 1: Q1w Challenge	q1w Dose 2	Week 2: Q1w Challenge	
			CAN	Challenge 1: Days 1 to 3 Challenge 2: Days 4 to 6 2038 q1w 32mg		Challenge 3: Days 8 to 10 Challenge 4: Days 11 to 13 Discharge: Day 14	
	MS-IR (QID)	morning of the Qual	CAN	12038 q1w 24 mg			
		Challenge					
2 weeks	Day -10, Day -9, Day -8, Day -7, or Day -6 to Day -4	Days - 3 to -1	Day 0	Days 1 to 6	Day 7	Days 8 to 14	Day 21

IR = immediate-release; MS = morphine sulfate; q1w = once weekly dosing; R = randomization

**Table 4** Schedule of Assessments

Screening		Inpatient Qualification Phase				Follow-up Phone Call				
Visit:	1 2									
Day:	-39 to -11	-10, -9, -8, -7, OR -6	-9, -8, -7, -6, OR -5 to -4	-3 to -1	0	1 to 3 & 4 to 6	7	8 to 10 & 11 to 13	14/ ET	21
Assessment										
Informed Consenta	X									
Eligibility Criteria Review b	X	X								
Medical and Medication History	X	Xc								
DSM-V	X									
Physical Examination (including BMI)	X d	Xe							Xe	
Serology panel (optional)	X									
Concomitant Meds/Procedures	X	X	X	X	X	X	X	X	X	X
ECG	X	X			Xf		Xf		X	
Urine Drug Screen g	X	X								
Breath Alcohol Test	X	X								

<sup>a Subjects must voluntarily provide written informed consent prior to any study-related procedures being performed.

Version: 2.0, 17NOV2015 Page 37 of 99

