Severity of Opioid Withdrawal VAS					X dd		X			
Check-in		X								
Discharge									Xee	

BMI=body mass index; COWS=Clinical Opiate Withdrawal Scale; C-SSRS=Columbia-Suicide Severity Rating Scale; DSM-V = Diagnostic and Statistical Manual of Mental Disorders – Fifth Edition; ECG=electrocardiogram; ET=Early Termination; FSH=Follicle Stimulating Hormone; HIV= Human Immunodeficiency Virus; MADRS=Montgomery-Asberg Depression Rating Scale; OOWS=Objective Opioid Withdrawal Scale; PD=pharmacodynamic VAS=visual analog scale.

- y Blood samples will be taken pre-dose and 1, 4, 6 and 8 hours after CAM2038 q1w injection
- z Blood samples will be taken approximately 60 minutes prior to administration of hydromorphone on each of the 3 Hydromorphone Challenge Session days during the Treatment Phase (i.e., Days 1, 2, 3, 4, 5, 6, 8, 9, 10, 11, 12, and 13).
- aa Blood samples will be taken approximately 168 hours after CAM2038 q1w injection
- bb Pharmacodynamic training may be administered as frequently as required, but all subjects must complete at least one training session prior to the Qualification/Baseline Hydromorphone Challenge Session. Training can only occur prior to or after, but not during the Hydromorphone Challenge Sessions.
- cc On Hydromorphone Challenge Session days (i.e., Day -3, -2, -1, 1, 2, 3, 4, 5, 6, 8, 9, 10, 11, 12, and 13), subjective measures (Drug Liking, Feeling High, Any Drug Effects, Good Drug Effects, Bad Drug Effects, Sedated, Desire to Use Opioids VAS) assessments will be performed at predose (up to 15 minutes prior to dosing) and at 5, 10, 15, 30, 45, 60, 75, 90, 120, 150, 180, 210, 240, 270 and 300 minutes post-dose.
- dd Severity of Opioid Withdrawal VAS will be administered, as needed, if a subject experiences precipitated withdrawal following administration of CAM203 q1w.
- ee Subjects will be discharged on Day 14, if medically acceptable.

Version: 2.0, 17NOV2015 Page 40 of 99

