Initial parenteral doses of hydromorphone for analgesia are 1 to 2 mg subcutaneously or IM every 2 to 3 hours PRN (Handelsman et al., 1987; Hydromorphone, 1984). However, supratherapeutic doses are needed for challenge studies in opioid abusers. Typically, a lower range of supratherapeutic doses can be employed in opioid abusing individuals without physical dependence and still produce robust dose-related effects. However, higher supratherapeutic doses are needed when investigating responses in active opioid abusers with physical dependence (and hence, higher levels of tolerance). Studies that have examined the ability of BPN maintenance treatment to produce blockade of hydromorphone effect have varied. For example, one openlabel trial of a depot BPN formulation examined hydromorphone doses of 0 mg and 3 mg (on the low end), but this product produced BPN plasma concentrations of under 2 ng/mL (a target range generally accepted as the lower therapeutic concentration for blockade, but effective for withdrawal suppression). Other studies have employed higher hydromorphone doses during BPN and methadone maintenance treatment ranging between 10 mg to 18 mg. In one early study, BPN SL solution (estimated to have approximately 30% higher bioavailability over the currently marketed tablets) (Handelsman et al., 1987; Hydromorphone, 1984) examined blockade with BPN maintenance doses ranging from 2 mg to 16 mg/day using a cumulative SC hydromorphone dosing procedure of 0 mg, 6 mg, and 12 mg, for a total challenge dose of 18 mg. A recent study examining blockade with another sustained-release BPN product (RBP 6000, Clinical Trials.gov, NCT02044094) examined single acute doses of 0 mg, 6 mg and 18 mg. Based upon prior studies of methadone and BPN maintenance, the proposed doses are appropriate for opioid challenge studies, should be safely tolerated during the Qualification Phase and should reflect attenuated responses after stabilization on BPN.

CAM20138 q1w doses of 24 mg and 32 mg were selected to represent a range of therapeutic doses that are being evaluated in Phase III efficacy studies.

Version: 2.0, 17NOV2015 Page 51 of 99

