9.1.2 PRIMARY ANALYSIS

The primary analysis of the primary efficacy variable, E_{\max} of drug liking VAS, will be performed using the completer population. This variable will be analyzed via a mixed model including sequence (ABC, ACB, BAC, BCA, CAB, CBA), dosing (challenge dosing A=0 mg, B=6 mg, or C=18 mg), period (1, 2, or 3 to indicate first, second, or third day of each challenge session), session (challenge session 1, 2, 3, or 4), and dosing-by-session interaction as fixed effects, and subject as random effects. The maximum likelihood estimation will be used to estimate the parameters. Specifically, the following pseudo SAS codes will be used for the analysis:

```
proc mixed data=Efficacy_Data method=ml;
class SubjectID ChallengeDose Sequence Period Session;
model Emax=Sequence ChallengeDose Period Session ChallengeDose*Session;
random SubjectID / Subject= SubjectID;
LSMEANS ChallengeDose*Session/diff cl alpha=0.05;
Run;
```

The estimated treatment effects, differences in treatment effects (test dose – the reference dose of 0 mg), 95% confidence intervals of the differences will be presented. Blockade effects will be claimed if the upper bound of the treatment difference is ≤ 11 .

The same methodology will be used to analyze CAM2038 q1w 24 mg and 32 mg separately.

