10.0 SUMMARIES OF PHARMACOKINETIC ANALYSIS

Pharmacokinetic endpoints include:

The following pharmacokinetic parameters will be estimated for BPN and norbuprenorphine:

- C_{\max} (maximum plasma concentration)
- C_{trough} (plasma concentration level 7 days after the latest injection)
- C_{av} (average plasma concentration during a dosing interval)

C_{av} will be calculated as (AUC_{0-168h}/τ) , where AUC_{0-168h} is the area under the plasma concentration-time curve (AUC) between time 0 and 168 hours after latest injection and τ the dosing interval (168 hours). AUC_{0-168h} will be calculated using the linear trapezoidal method up to C_{\max} and the logarithmic trapezoidal method for the remainder of the curve up to 168 hours after latest injection.

The PK parameters will be calculated using Phoenix WinNonlin Version 6.3 (or higher). The actual sampling times relative to dosing rather than the nominal times will be used in the calculations. BPN and norbuprenorphine plasma concentrations over time as well as all above PK parameters will be summarized by dose (32 mg and 24 mg) separately.

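### Blockade is tested only to about 144 h of a 168 h dosing interval, and each late-week estimate averages three days, so the duration conclusion should be limited to the tested window

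*Protocol*

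**What the plan says.** Protocol 7.1 gives the purpose of the study as to "evaluate the degree and duration of action of multiple doses of CAM2038 q1w". Section 7.1.3 schedules the challenges at "approximately 24, 48, 72, 96, 120, and 144 hours" after each injection, with pharmacodynamic ratings for up to 5 h. Section 7.2 describes this schedule as running to "144 hours post-dose in order to investigate the full duration and magnitude of opioid-blockade of the CAM2038 q1w formulation".

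SAP 10.0 takes the dosing interval as 168 h. Day 7 is the second injection day and Day 14 is discharge. For Day 14, Table 4 provides a pharmacokinetic sample ("Blood samples will be taken approximately 168 hours after CAM2038 q1w injection") but no challenge and no VAS battery.

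Each session gives 0, 6 and 18 mg on three consecutive days in one of six orders. The SAP 9.1.2 model has fixed effects for sequence, dose, "period (1, 2, or 3 to indicate first, second, or third day of each challenge session"), session, and dose-by-session, with subject random. Differences from 0 mg are reported per session, and blockade is claimed if the upper 95% bound is at most 11. There is no dose-by-period or dose-by-day term. The planned efficacy figures are by session, and SAP 9.5 leaves PK/PD to be explored as appropriate.

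On exposure, Section 7.1.5 says that at the end of the Treatment Phase "plasma BPN levels are expected to be approximately 1.4 to 1.8 ng/mL".

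**The concern.** For a weekly depot, the duration question is whether blockade lasts until the next injection. Two features limit the answer. The last 24 h of the interval, 24/168 = 14% of it, begin at the final challenge, and ratings stop at about 149 h. And the late-week evidence is a three-day average centred on 120 h. If blockade weakens towards the end of the week, that average understates the effect on the last tested day, and nothing is observed after it.

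At stake is the wording of the conclusion. Passing results for Sessions 2 and 4, set beside the statement in Section 7.2, could be reported as blockade throughout the week.

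**Working it through.** **1. The plan's own power.** Inputs from Protocol 12.1 and SAP 9.6: n = 24 per CAM2038 group, SD 9.8, margin 11, two-sided 0.05, true difference 1.5 (32 mg) or 2.5 (24 mg). A two-sample noncentral t calculation (24 v 24, df 46) gives 90.8% and 83.7%, against the stated 90% and 83%. So the planning figures treat the hydromorphone doses as independent groups:

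SE = 9.8 × √(2/24) = 2.83.

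A within-subject correlation of 0.5 (my assumption; the documents give none) would give SE = 9.8 × √(2 × 0.5/24) = 2.00.

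**2. What a session contrast estimates.** With 24 subjects over six sequences there are 4 per sequence. Each dose is last in 2 of the 6, so 8 subjects receive a given dose on a given day. Each dose falls on each day in one third of subjects, and period is additive. The session contrast is therefore the mean of the three day-specific differences: 96, 120 and 144 h in Sessions 2 and 4.

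**3. Dilution of a last-day loss.** Hold the true difference at 1.5 at 96 and 120 h and let it be d at 144 h. Session mean m = (1.5 + 1.5 + d)/3, and P(upper bound ≤ 11) = Φ((11 − m)/SE − 1.96).

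| d at 144 h | m | P, SE 2.83 | P, SE 2.00 |
|---|---|---|---|
| 15 | 6.0 | 42% | 70% |
| 20 | 7.67 | 22% | 39% |
| 25 | 9.33 | 9% | 13% |

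For d = 15: (11 − 6)/2.83 − 1.96 = −0.19, giving 42%. Simulating the session model by least squares (24 subjects, four per sequence) gave 41% under independence and 62 to 67% with correlation 0.5. The true session mean reaches 11 only at d = 30, since (1.5 + 1.5 + 30)/3 = 11. These probabilities are per session; the SAP does not say whether all four sessions must pass.

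**4. Exposure at the end of the week.** Protocol Table 2 gives 168 h levels after one dose of 0.86 ng/mL (24 mg, predicted) and 1.1 ng/mL (32 mg). Table 3 predicts steady-state troughs of 1.4 and 1.8 ng/mL. For 32 mg after the first dose:

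- Log-linear from 3.76 ng/mL at 36 h (Table 1) to 1.1 at 168 h: k = ln(3.76/1.1)/132 = 0.0093 per h. The level at 144 h is 3.76 × exp(−108k) = 1.38, and the fall from 144 to 168 h is 1 − exp(−24k) = 20%.
- This line implies AUC to infinity of about 140 (0–36 h, trapezoid on Table 1) + 2.66/k = 286 (36–168 h) + 1.1/k = 118 (tail) = 544, against 638 in Table 2. Matching 638 needs a tail of 638 − 140 − 286 = 212, so k = 1.1/212 = 0.0052 and a fall of 1 − exp(−24 × 0.0052) = 12%.

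The further fall after the last challenge is therefore roughly 12 to 20%, depending on the assumed decline.

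**5. Precision of a 144 h contrast.** In one week, 8 subjects per dose give SE = 9.8 × √(2/8) = 4.9 and a half-width of about 10 (1.96 × 4.9 = 9.6; 10.5 with t on 14 df). At a true difference of 1.5 the bound would meet 11 with probability Φ(9.5/4.9 − 1.96) = 49%; at zero, Φ(11/4.9 − 1.96) = 61%. Using both weeks gives 16 observations per dose: 9.8 × √(2/16) = 3.46, half-width 6.8, if they are treated as independent.

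**The case against.** The strongest reply is that no full-week claim is tested. The primary objective concerns the degree of blockade. The decision rule and the ordered comparisons in SAP 9.4 contain no duration hypothesis, and the challenge times are stated openly. That stands, and it is why this point is about the duration conclusion and not the primary test.

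The SAP also handles part of the problem. Its dose-by-session term gives Days 4–6 and Days 11–13 separate estimates. A reader might infer that the analysis merges the two late sessions, or that any late-week failure would go unseen; the SAP model does not support either reading. A loss over the whole late half-week, or a very large one on the last day, would show.

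A reader might also take Section 9.4 to mean that blockade must fail late in the week, because it refers to levels "under 2 ng/mL (a target range generally accepted as the lower therapeutic concentration for blockade". That remark is background about another depot product, and its wording is ambiguous. It is not a criterion of this trial. On the log-linear curve the 32 mg level passes below 2 ng/mL at 36 + ln(3.76/2)/0.0093 = 104 h, so the 120 and 144 h challenges already sample that region.

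Finally, day-level contrasts are too imprecise to decide anything: at planning precision, even complete blockade would miss the limit at 144 h in about 39% of trials. That limits the remedy to a descriptive one.

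**Conclusion.** The point holds in limited form. Section 7.2 overstates the coverage: the design tests about 24 to 144 h after injection, and no reanalysis can supply challenge data for 168 h. Within the tested window, the late-session estimates are three-day averages. A last-day difference of 15 points, above the margin, would pass in a given session about 42% of the time on the planning assumptions and about 70% with correlation 0.5. Those figures assume that the loss is confined to the last day. The low 168 h levels make the end of the week the period of most interest, but they do not show that blockade is lost there.

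A gradual rise is a weaker case. With differences of 0, 5 and 10 over the three days, no tested day exceeds 11, the mean is 5, and the rule passes about 56% of the time (Φ(6/2.83 − 1.96)). Extending that line to 15 at 168 h would be extrapolation with no support in the documents. Nor do the documents support reading this point as invalidating the primary blockade claim.

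**What to change.** 1. In Protocol 7.2, replace the full-duration statement. Limit the duration conclusion to about 24 to 144 h after injection, and state that blockade was not tested at 168 h.
2. In SAP 9.1.2, add for each CAM2038 group a supportive, descriptive model with hydromorphone dose by day since injection, either pooled over both weeks or as a linear day slope within dose. Report the 6 mg and 18 mg differences from 0 mg at 144 h, with 95% confidence intervals, beside the session averages. State in advance that these estimates qualify the duration statement and do not decide it.

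The primary test, margin and testing order stay as they are, and no new data are needed. The cost is a narrower duration statement and wide intervals (half-width about 10 points from one week). Pooling the weeks narrows them but averages over first-dose and second-dose exposure, and the slope model assumes a linear trend over the days; the report should say so.
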